Study design	Open label, single-center, single-dose, diagnostic imaging efficacy study

Methodology	
Participating subjects already underwent a clinically indicated prostate MRI resulting in at least one PI-RADS 3-5 lesion performed within 3 months prior to recruitment.
 
Research imaging: ^{68}Ga-PSMA PET/CT.
 
Fusion of mpMRI and ^{68}Ga-PSMA PET and biopsy target selection from mpMRI and ^{68}Ga-PSMA PET.
 
Prostate biopsy procedure (clinically indicated): standard biopsy and additional targeted biopsies to obtain pathological proof. Biopsy targets are selected from mpMRI and ^{68}Ga-PSMA PET.

Type of control	Not applicable
Number of subjects	100
Safety Assessments	Patient vital signs will be taken before and after the administration of the radiopharmaceutical. The patients will also be asked to report adverse events.
Plan for statistical analysis	
Visual and semi-quantitative assessment of PET/CT images: Descriptive statistics, frequency tables.
 
We employ mixed effects logistic regression model to estimate the positive likelihood ratio (LR) of the combination of ^{68}Ga-PSMA-guided plus mpMRI-guided biopsy (fusion PET/MRI) for the detection of primary Gleason $\geq 3+4$ cancer is higher than for mpMRI-guided biopsy (using PI-RADS version 2) alone.

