5 STUDY OBJECTIVES AND PURPOSE

The primary study aim is the prospective comparison of standard-of-care mpMRI vs. combined ⁶⁸Ga-PSMA PET and mpMRI (⁶⁸Ga-PSMA fusion PET/MRI) for the detection and risk-stratification of clinically significant primary PCa.

Following (clinical) mpMRI and (research) ⁶⁸Ga-PSMA PET/CT imaging, we will perform targeted and standard 12-sample prostate biopsies. Biopsy targets will be defined from mpMRI and ⁶⁸Ga-PSMA PET; mpMRI interpretation will be done in accordance with PI-RADS v2.

Primary objective: We will determine the sensitivity and specificity of mpMRI alone and mpMRI in combination with ⁶⁸Ga-PSMA PET (i.e., fusion PET/MRI) for the detection of primary Gleason $\geq 3+4$ PCa. Primary outcome measure: determination whether the positive likelihood ratio (LR) for ⁶⁸Ga-PSMA PET-MRI is at least 1.28 greater than that of standard-of-care mpMRI. Reference standard will be pathology defined as targeted plus standard prostate biopsy, and prostatectomy, when available.

Secondary objective: We will determine the safety of ⁶⁸Ga-PSMA. We will also determine frequency and location of ⁶⁸Ga-PSMA positive lesions, such as potential extra-prostatic extension, lympho-nodal and/or distant metastatic disease positive on ⁶⁸Ga-PSMA but not identified by conventional (standard) imaging. While histological verification would be desirable, the decision for or against tissue verification will depend on clinical decisions making only, and not be required due to study participation.

Exploratory objective: We will evaluate whether radiomics classifiers (obtained from mpMRI and ⁶⁸Ga-PSMA identified targets) could improve identification and risk stratification of significant PCa. Reference standard will be pathology defined as targeted plus standard prostate biopsy, and prostatectomy, when available.

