12 STATISTICAL EVALUATION

Accrual potential: At the University of Michigan, over 800 patients receive a prostate biopsy per year (812 in 2016, 652 in 2015, 444 in 2014). The number of navigated TRUS-MRI fusion (targeted) prostate biopsies is rapidly increasing and reached 310 in 2016. In 2016, the Department of Radiology performed 960 mpMRI studies, of which about 60% (576) had a PI-RADS score ≥ 3 .

Prevalence of significant PCa: Among all patients with PI-RADS score ≥ 3 , the incidence of Gleason $\geq 3+4$ PCa is 15% for PI-RADS 3, 55% PI-RADS 4, and 80% PI-RADS 5. At our center, the sensitivity/specificity for Gleason $\geq 3+4$ is 96.5/59.7% for PI-RADS ≥ 3 , and 78.9/78.9% for PI-RADS ≥ 4 . The patient population for this trial will closely resemble a recently retrospectively investigated surveillance population from 2 centers in the state of Michigan (n=207) of men with clinical stage T1/T2 Gleason 3+3 PCa. The distribution of PI-RADS grading was as follows (unpublished data): PI-RADS 1-2 (37%), PI-RADS 3 (19%), PI-RADS 4 (31%), PI-RADS 5 (13%). This incidence of PI-RADS scores ≥ 3 is used in **Table 1** to estimate the incidence of Gleason 3+3 vs. $\geq 3+4$ vs. benign findings in the trial population. Since we will only select patients with prior mpMRI resulting in PI-RADS 3-5, we will be able to select a specific relevant patient population with a sufficient risk for significant disease (defined as Gleason $\geq 3+4$ PCa).

Disease incidence in study population: We estimate the potential impact of molecular imaging in addition to mpMRI for this trial on the basis of our prior ^{18}F -choline PET/MRI trial.¹⁶ Our final (submitted) data included 90 PI-RADS 3-5 lesions in 56 subjects resulting in 30 “positive” (Gleason $\geq 3+4$) and 60 “negative” (Gleason 3+3 or benign). Using a logistic regression model with two predictors—MRI suspicion score and a ^{18}F -choline lesion-to-background ratio of ≥ 1.58 (AUC = 0.95)—strongly favored the combined model over the mpMRI model alone (AUC = 0.83, $p < 0.001$). The selection of all PI-RADS ≥ 4 lesions for the prediction of Gleason $\geq 3+4$ PCa resulted in an excessive number of false-positive ($n = 27$ [FP]) and false-negative ($n=3$ [FN]) cases. When selecting PI-RADS 5 lesions only, 3 FP and 11 FN cases would have resulted, which indicates missing too many significant cancers. The addition of ^{18}F -choline PET to mpMRI resulted in 5 FP and 5 FN cases.

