Primary objective: Mixed-effects logistic regression is used to evaluate the primary objective, the diagnostic performance of mpMRI and PET. The outcome is Gleason $\geq 3+4$ or not, and predictors are PI-RADS v.2 score and ^{68}Ga -PSMA PET uptake. We employ a mixed effects model to account for within-subject correlation among one or more biopsied lesions. We will test the null hypothesis that the regression coefficient of PET is equal to zero versus an alternative hypothesis that it is not equal to zero, assessing whether ^{68}Ga -PSMA PET is an important factor to identify aggressive PCa. We also compare predictive accuracies of (1) PI-RADS ≥ 3 only and (2) PI-RADS ≥ 3 plus ^{68}Ga -PSMA PET models by examining the confidence intervals of a predictive performance measure: positive likelihood ratio (positive LR).

Secondary objectives: We are not expecting any adverse events related to the administration of the radiotracer. However, frequency tables will be generated to display the safety profile of ^{68}Ga -PSMA (secondary objective).

We will also record the frequency and location of extra-prostatic ^{68}Ga -PSMA positive lesions (such as extra-prostatic extension, lympho-nodal and/or distant metastatic disease) not identified by conventional (standard) imaging. Formal statistical evaluation is not planned as the frequency of such findings is expected to be low.

Exploratory objective: We will evaluate whether radiomics classifiers (obtained from mpMRI and ^{68}Ga -PSMA identified targets) could improve identification and risk stratification of significant PCa. Reference standard will be pathology defined as targeted plus standard prostate biopsy, and prostatectomy, when available. The performance of the different classifiers in detecting significant PCa will be evaluated by using the area under the receiver-operating characteristic (ROC) curve (AUC) using pathology as gold standard.⁵⁷

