12.1 Sample size determination

Sample size calculation was made for the primary objective only. We assess potential differences between the predictive performances of the two models (1) and (2), while maintaining ethical and economic considerations. We consider the positive likelihood ratio (positive LR) as a performance measure, which is defined by a ratio of sensitivity to 1-specificity. A higher positive LR means greater predictive information of positive test results irrespective of disease prevalence. Based on preliminary data obtained from mpMRI, we assume that the sensitivity and specificity of model (1) are both given by 0.789. For model (2), we assume conservatively that the sensitivity will be increased by 0.02 (2%) and that the specificity would improve by 0.15 (15%). In this scenario, the positive LR of model (1) is given by 3.74 and the positive LR of model (2) is calculated as 5.02. In order to detect the 1.28 difference in positive LR between the two models, we need at least 100 subjects, including at least 38 of 100 subjects with a histological diagnosis of significant PCa. The sample size was estimated as described in the literature.⁵⁸

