12.5.2 Analysis of Primary Endpoints

PET images will initially be interpreted by a board certified nuclear medicine physician or a board-certified radiologist experienced in reading PET at the time of the imaging study at Michigan Medicine. Upon request, case report forms and coded ⁶⁸Ga-PSMA PET/CT imaging data will be provided to the FDA for review.

Intraprostatic lesions identified by mpMRI as PI-RADS 3-5 will be graded visually on a two-point scale as either positive or negative for elevated ⁶⁸Ga-PSMA uptake relative to prostatic gland uptake (0=Negative or 1=Positive).

Any focal intraprostatic elevated ⁶⁸Ga-PSMA uptake relative to prostatic gland that was not identified by mpMRI (as PI-RADS 3-5) but was targeted at biopsy will also be evaluated visually as either positive or negative (0=Negative or 1= Positive).

All subjects with histopathology correlates will be analyzed for the primary aim. Sensitivity and specificity, positive and negative predictive values, and accuracy (along with the corresponding two-sided 95% confidence intervals) will be determined on a per-subject and per-lesion basis for ⁶⁸Ga-PSMA-11 PET and mpMRI regarding the detection of Gleason \geq 3+4 cancer. Standard reference of truth is histopathology from all individual biopsy cores, targeted and standard cores.

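### The primary outcome (LR+ at least 1.28 higher for fusion PET/MRI) is not carried into a matching analysis or decision rule, and 1.28 does not follow from the plan's own inputs

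*Combined protocol and SAP*

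**What the plan says.** Section 5 (and the Synopsis objective) makes the primary outcome whether LR+ for "PET-MRI is at least 1.28 greater than that of standard-of-care mpMRI". The Synopsis paragraph on statistical analysis drops the margin and asks only whether LR+ for detecting Gleason ≥3+4 "cancer is higher than for mpMRI-guided biopsy (using PI-RADS version 2) alone".

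Section 12, Primary objective, fits a mixed-effects logistic model with PI-RADS score and PET uptake as predictors and a random effect for lesions within a subject. Its one formal hypothesis is: "We will test the null hypothesis that the regression coefficient of PET is equal to zero", against a two-sided alternative. It then compares a model with PI-RADS ≥3 only and a model with PI-RADS ≥3 plus PET, looking at these two "models by examining the confidence intervals of a predictive performance measure: positive likelihood ratio (positive LR").

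Section 12.1 uses 1.28 differently, as an effect to be detected: "In order to detect the 1.28 difference in positive LR between the two models, we need at least 100 subjects". The figure comes from 3.74 for model (1) and the statement that "the positive LR of model (2) is calculated as 5.02".

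Section 12.5.2, headed as the analysis of the primary endpoints, says: "Sensitivity and specificity, positive and negative predictive values, and accuracy (along with the corresponding two-sided 95% confidence intervals) will be determined", per subject and per lesion, for PET and for mpMRI. It grades PET as 0 or 1. It does not mention LR+, 1.28 or a combined PET/MRI reading. Section 12.2 sets 0.05 for all tests. Section 11.1 refers to the statistical analysis plan; in the combined document that content is sections 11 and 12.

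**The concern.** A trial with a numerical primary criterion needs an analysis that answers it. Here the test and the criterion are different questions. A non-zero PET coefficient shows that uptake is associated with Gleason ≥3+4 given PI-RADS. It fixes no positivity threshold and implies no particular change in LR+. The trial could therefore report a significant primary test and leave its declared question open.

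The LR+ comparison does not fill the gap. The text does not say whether the interval is for each LR+, their difference or their ratio, or what it must exclude. Read literally, section 5 is a point-estimate criterion that ignores uncertainty. The same data could then count as success or failure under a rule chosen after they are seen.

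Two further gaps feed into this. The threshold rests on an arithmetic error, and the two readings being compared are not settled.

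**Working it through.** **1. The plan's own figure.** Section 12.1 defines LR+ = sensitivity/(1 − specificity).
- Model (1), both 0.789: 0.789/0.211 = 3.74. This reproduces.
- Model (2), sensitivity +0.02 and specificity +0.15: 0.809/(1 − 0.939) = 0.809/0.061 = 13.26, not 5.02. The difference is 13.26 − 3.74 = 9.52, not 1.28.
- 5.02 is obtained with specificity +0.05: 0.809/0.161 = 5.02.

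**2. Precision at 38 diseased and 62 non-diseased (section 12.1).** Var(log LR+) = (1/Se − 1)/38 + (1/FPR − 1)/62, with FPR = 1 − specificity.
- LR+ 3.74: 0.00704 + 0.06031 = 0.06735, SE 0.260, 95% CI 2.25 to 6.22.
- LR+ 5.02: 0.00621 + 0.08405 = 0.09026, SE 0.300, 95% CI 2.79 to 9.05.

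The intervals overlap heavily, so the meaning of examining them decides the answer.

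**3. Chance of declaring success under natural readings of the text.** Simulated paired binary readings, per subject, 38/62. The ranges run over assumed dependence, from independent to fully concordant readings (for equal readings, to strongly concordant).

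| Rule | True 3.74 vs 5.02 | True 3.74 vs 13.26 | Both truly 3.74 |
|---|---|---|---|
| Point difference ≥1.28 | 44-50% | 98-100% | 2-19% |
| Paired 95% CI of LR+ ratio above 1 | 9-42% | 62-98% | at most about 3% |
| Separate 95% CIs do not overlap | 0-1.5% | 19-28% | about 0% |

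The sample size tells the same story. On the log scale, N = 100 × [(1.96 + 0.84) × SE/d]², where d is the log of the LR+ ratio and SE is that of the difference in log LR+ at 38/62. For 3.74 vs 5.02, d = 0.295. With independent readings SE = √(0.06735 + 0.09026) = 0.397, and N is about 1,417 for two-sided 80% power. With an assumed correlation of 0.7 it is about 438. For 3.74 vs 13.26 the range is about 158 down to 70. Section 12.1 states no power, so its 100 could not be reproduced.

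**4. The mpMRI cut-off.** Section 12 labels model (1) PI-RADS ≥3. The 0.789/0.789 used in section 12.1 is the centre's accuracy for PI-RADS ≥4; for ≥3 section 12 gives 96.5%/59.7%, an LR+ of 0.965/0.403 = 2.39. Section 7.2 admits only men with at least one PI-RADS 3-5 lesion. Per subject at ≥3, sensitivity and false-positive rate are therefore both 1, and LR+ = 1.

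**5. The fusion reading and the unit.** PET is binary in section 12.5.2, and section 9.2.1 suggests a threshold of 2 SD above prostate background. No text says which combinations of PET and PI-RADS count as fusion-positive. The section 12 model works on lesions; section 12.5.2 reports both units and names neither as primary.

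**6. Why an LR+ contrast alone is not enough.** In the prior choline trial (section 12: 30 positive and 60 negative lesions), PI-RADS ≥4 gave 27 FP and 3 FN, hence 27 TP. For the stricter cut-off, "When selecting PI-RADS 5 lesions only, 3 FP and 11 FN cases would have resulted", hence 19 TP. The paired LR+ ratio is (19/27)/(3/27) = 6.33. SE(log) = √(1/19 − 1/27 + 1/3 − 1/27) = 0.558, 95% CI 2.1 to 18.9. A rule that asks only for a lower limit above 1 would be met with no PET information, while sensitivity falls from 27/30 = 90% to 19/30 = 63%. These counts are illustrative: section 4.1 splits the same 90 lesions 40/30/20, so 50 and 20 lie above the two cut-offs, against 54 and 22 here.

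**The case against.** The strongest reply is that LR+ is not ignored. A comparison of intervals is planned, LR+ follows from the sensitivity and specificity listed in section 12.5.2, and section 5 can be read as a complete criterion: the estimated gain is at least 1.28 or it is not. Most of this stands. A reader might infer that the plan omits LR+ or has no criterion at all; the documents do not support that. What they lack is a criterion that allows for uncertainty and is carried into section 12.

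Other stronger readings also go too far:
- **mpMRI LR+ must be 1 in this trial.** This holds per subject at PI-RADS ≥3. It does not hold for lesion-level data that include PET-only targets and standard cores, which can be mpMRI-negative.
- **Positivity is undefined for both readings.** The mpMRI cut-off is inconsistent rather than absent, and PET is graded 0/1. The missing piece is the fusion rule.
- **A gain of 1.28 is out of reach in the enrolled population.** This requires moving the +2/+15 point projection to baselines that section 12.1 did not use. On section 12.1's own inputs the gain is 9.52.
- **The choline counts show that the gain can change sign with the mpMRI cut-off.** A negative gain needs PI-RADS 5 alone as the comparator, a cut-off that section 12 itself rejects, and the counts conflict with section 4.1.

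Per-lesion success rates can also be simulated, but the lesion mix and correlations would be assumed. The conclusion does not rest on them.

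**Conclusion.** The point holds. The declared primary outcome has no matching test, interval or uncertainty-based success rule in section 12. Its threshold is wrong as written (a difference of 9.52 on the stated inputs, against 1.28). The mpMRI cut-off conflicts between the model label and the sample-size input, the fusion rule is missing, and the primary unit is not named.

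At the stated 3.74 vs 5.02, the choice of rule alone moves the chance of success from near zero to about one half. If PET adds nothing, the point rule still succeeds in about 2-19% of trials. These percentages are per subject at 38/62 and depend on the assumed dependence between readings; the upper end for the paired ratio (42%) needs full concordance and is optimistic. The textual gaps and the arithmetic error depend on no assumption. This should be settled before pathology results are analysed.

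**What to change.** (a) Correct 5.02 and 1.28 in the Synopsis, section 5 and section 12.1, and restate what 100 subjects with 38 diseased can detect. Treat 1.28 as a planning effect, not a success margin.

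(b) In section 12.5.2 name one primary unit and one paired contrast of fusion vs mpMRI LR+. One option is the LR+ ratio with a 95% CI from a bootstrap that resamples whole subjects, with a stated rule for zero false positives. Success requires a lower limit above 1.

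(c) Success must also require a pre-stated paired condition that sensitivity is not materially reduced, and a significant PET coefficient given PI-RADS. A stricter cut-off alone then cannot succeed. Report paired sensitivity and specificity beside LR+.

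(d) Before pathology is known, fix one mpMRI cut-off that varies among the enrolled subjects or lesions, and one fusion rule. If fusion positivity comes from a fitted model, score it out of sample by cross-validation or with an optimism correction. Refitting in each resample does not by itself remove the optimism.

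(e) Align the Synopsis, section 5, section 12 (Primary objective), section 12.1 and section 12.5.2.

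The cost is SAP wording and some programming, with no added patient procedures. The stated detectable effect for 100 subjects becomes less favourable, and the sample size must be revisited if 3.74 vs 5.02 remains the target.

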12.5.4 Analysis of the Exploratory Objective

Radiomics analyses will be performed retrospectively, thus after prostate biopsies have been performed. Accordingly, radiomics analysis results will not be used to identify targets for prostate biopsies.

Radiomics analysis consists of two steps: (1) Image feature extraction and (2) Model building of discriminant classifiers.⁵⁰ We plan to extract intensity, texture and morphological features from ⁶⁸Ga-PSMA PET and mpMRI⁴⁶ into mathematical models using advanced machine-learning methods while accounting for confounding effects from clinical parameters (stage, age, histology, etc.).⁵⁹ For feature extraction we will assess co-registered T1w, T2w, ADC, DCE MRI, and ⁶⁸Ga-PSMA PET volumes. Specific image features related to tumor heterogeneity include: (a) first-order histogram intensity variations (mean, min, max, variance, skewness, etc.); (b) shape (eccentricity, solidity, etc.), and (c) texture features (second order histogram metrics), which relate intensity to local spatial distribution using matrix methods such as the gray-level co-occurrence matrices (GLCM) and others such as neighborhood gray-tone difference matrix (NGTDM), run-length matrix (RLM), and grey-level size-zone matrix (GLSZM) features on PET,⁴⁶ PET/CT,⁶⁰ and separate or fused PET/MRI.⁶¹ Image pre-processing of VOIs involves feature enhancement (denoising/deblurring) and rescaling to isotropic voxels.^{46,50}

We will explore advanced statistical learning methods to build maximally discriminant classifiers of significant PCa (Gleason \geq 3+4). Different machine learning classifiers using linear generalized models (Elastic net), support vector machine (SVM), random forests (RF), and deep learning (convolutional neural network (CNN)) techniques may be employed.^{62,63}

Methods based on statistical resampling and information theory will be used to guard against over-fitting and to evaluate generalizability to out-of-sample data.⁶⁴ Feature-based classifiers (LASSO, SVM, RF, NN, DNN) and featureless classifiers (CNN) may be applied as well.

2. Boutros, P.C., et al. Spatial genomic heterogeneity within localized, multifocal prostate cancer. *Nat Genet* **47**, 736-745 (2015).

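### The exploratory radiomics aim asks about improvement, but its only stated measure is each classifier's own AUC, with no PI-RADS plus 68Ga-PSMA uptake reference to improve upon

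*Combined protocol and SAP*

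**What the plan says.** Sections 5 and 12 state the exploratory objective in the same terms: whether radiomics classifiers built from mpMRI and 68Ga-PSMA targets "could improve identification and risk stratification of significant PCa". Neither says what they should improve upon. Section 12 then gives the measure: "The performance of the different classifiers in detecting significant PCa will be evaluated by using the area under the receiver-operating characteristic (ROC) curve", judged against pathology.

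Section 12.5.4 describes the modelling. Features come from co-registered MRI sequences and from the 68Ga-PSMA PET volumes. They include "first-order histogram intensity variations (mean, min, max, variance, skewness, etc", together with shape and texture. Models are to be built "while accounting for confounding effects from clinical parameters (stage, age, histology, etc"; PI-RADS and the PET reading are not in that list. Resampling is planned to limit over-fitting.

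A comparison of PI-RADS with and without PET is planned only for the primary objective, and on the positive likelihood ratio. Nothing links it to radiomics.

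**The concern.** Asking whether something improves identification is a question about a difference. The AUC of one classifier against pathology answers another question: does this classifier separate significant from other lesions at all? Pathology supplies the truth, not a competing model. Ranking the radiomics classifiers against one another does not help either, since none of them represents what PI-RADS and uptake already achieve.

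The distinction matters here because PET intensity is itself among the radiomics inputs. If uptake discriminates, as section 4.1.1 expects, a classifier that has learned little beyond uptake will show a good AUC even when texture, shape and machine learning contribute nothing. The reader of the results could not tell which had happened. At stake is the interpretation of the exploratory aim only.

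**Working it through.** **1. Search for a comparator.** The documents give no AUC target, AUC difference or sample size for this objective (section 12.1 covers the primary objective only), so there is no planned figure to reproduce. The places that could name a reference model are:

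| Place | What it gives | Reference model for radiomics? |
|---|---|---|
| Synopsis | Exploratory assessment of texture analyses | No |
| 4.1.2 | Value unknown, to be assessed retrospectively | No |
| 5 | Improvement question; pathology as truth | No |
| 12, Exploratory objective | Improvement question; AUC against pathology | No |
| 12, Primary objective | PI-RADS with and without PET, on positive LR | Not linked to radiomics |
| 12.5.4 | Features, learners, clinical covariates, resampling | No |

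**2. PI-RADS alone, from Table 1.** Subjects with Gleason ≥3+4 at maximum PI-RADS 3/4/5 number 5/26/17 (total 48). The others, benign plus 3+3, number 26/22/4 (total 52). I used these cell counts; the first two rows sum to 31 and 48, against the printed 30 and 49. With half credit for ties:

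AUC = [5 × 13 + 26 × (26 + 11) + 17 × (26 + 22 + 2)] / (48 × 52) = (65 + 962 + 850) / 2496 = 1877 / 2496 = 0.752.

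**3. A score that only re-encodes uptake.** Assumptions, none of them in the documents: one lesion per subject; normally distributed uptake with equal variance in both groups and a true AUC of 0.80, 0.85 or 0.90; uptake independent of PI-RADS given disease status. The score is a monotone function of uptake, so its AUC equals that of uptake and its true added value is zero. The reference combines the Table 1 PI-RADS log likelihood ratio with uptake at its true weight. In 4,000 simulated trials per row (48 positive, 52 negative):

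| True AUC of uptake | Score's 95% CI above 0.5 | Score beats PI-RADS alone | Mean AUC, PI-RADS + uptake | Score minus reference |
|---|---|---|---|---|
| 0.80 | 100% | 76% | 0.869 | about −0.07 |
| 0.85 | 100% | 96% | 0.900 | about −0.05 |
| 0.90 | 100% | 99.8% | 0.931 | about −0.03 |

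So a score with nothing to add, and worse than the proper reference, still gives a respectable AUC.

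**4. Sensitivity to the assumed separation.** A second simulation used 160 independent lesions, a PI-RADS mix of 30/49/21% (Table 1), risks of 15/55/80% (section 12), and a score that is a noisy copy of uptake (reliability 0.6 to 0.9). The mix and risks are subject-level figures applied to lesions, and the 160 is assumed. The lower AUC limit exceeded 0.5 in practically every trial (99.8 to 100%). The zero-gain score beat PI-RADS alone in about 66 to 100% of trials at separations of 1.5 to 2.0 SD, but in only about 19 to 47% at 1.0 SD. A nested test of PI-RADS plus uptake, with and without the score, rejected in 4.4 to 6.6% of trials, close to the nominal 5%. The incremental question is therefore the one that recognises a null gain.

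**5. Precision of a single AUC.** The Hanley-McNeil variance is [A(1−A) + (n₁−1)(Q₁−A²) + (n₀−1)(Q₂−A²)] / (n₁n₀), with Q₁ = A/(2−A) and Q₂ = 2A²/(1+A). For A = 0.90, Q₁ = 0.8182 and Q₂ = 0.8526.
- 48 positive, 52 negative: SE = 0.0326; 95% CI 0.90 ± 1.96 × 0.0326 = 0.84 to 0.96.
- 38 positive (the minimum in section 12.1), 62 negative: SE = 0.0356; 95% CI 0.83 to 0.97.

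The illustrative reference AUCs of 0.869, 0.900 and 0.931 all lie inside both intervals. Even an AUC of 0.90 would not show a gain over PI-RADS plus uptake.

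**The case against.** The strongest reply is that this is an unpowered exploratory aim with modest wording. The synopsis calls it an assessment, and section 4.1.2 speaks of assessing the value of radiomics because its utility is unknown. AUC against pathology suits that purpose. That reading is open for those two places, but sections 5 and 12 state the objective as improvement, and the measure does not address it. The choice of PI-RADS plus uptake as comparator is a recommendation, since the text leaves the comparator open.

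Several stronger inferences are tempting and do not stand:
- A reader might infer that the plan will declare a false improvement. It sets no AUC threshold, test or success rule, so it makes no such declaration.
- A reader might infer that the intensity features are the same variable as the PET predictor in the primary model. Section 12.5.2 grades PET visually as 0/1, section 9.3.3 uses a 0 to 3 visual score, and section 9.2.5 refers to uptake measures. The features overlap with uptake; the documents do not make them identical to the primary predictor.
- A reader might infer that the result would be uninformative in either direction. A poor AUC would still be informative.
- A reader might take the AUCs of 0.83 and 0.95 in section 12 as the expected scale. They come from the earlier 18F-choline trial, whose results the plan itself says do not carry over directly to 68Ga-PSMA.

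It is also fair that PI-RADS, uptake and pathology are all collected, so the comparison could be added later. The reason to state it now is to prevent a favourable comparator from being chosen after the results are seen.

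**Conclusion.** The point holds as a mismatch between question and measure. The exploratory objective asks for improvement, the stated evaluation is stand-alone discrimination, and no reference model is named. Because PET intensity is among the features, a good AUC cannot be separated from what PI-RADS and uptake already provide. This conclusion rests on the text and not on the simulations. Those only illustrate it, and their size depends on the assumed uptake separation: at 1.0 SD the zero-gain score usually did not beat even PI-RADS alone. The primary and safety conclusions are untouched, and radiomics does not select biopsy targets. It is a worthwhile, inexpensive correction to an exploratory analysis.

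**What to change.** In section 12 (Exploratory objective) and section 12.5.4:

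1. Name PI-RADS plus 68Ga-PSMA uptake as the reference model and define how uptake enters it, for example as a continuous measure. Against a 0/1 visual read, a continuous intensity feature could gain simply by being less coarse, and that gain should not be credited to radiomics. State also what PI-RADS value is given to targets found on PET only.
2. On the same lesions, report the paired out-of-sample AUC difference between the reference and the reference plus radiomics, with a 95% CI from resampling whole subjects. Section 7.3 allows repeat participation, so keep all lesions and visits of one person together.
3. Base any statement that radiomics improves identification on that difference. Keep stand-alone AUCs as descriptive results.

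The cost is SAP wording and one extra model, with no new data or procedures. The apparent gain will be smaller than a stand-alone AUC suggests, and its interval will be imprecise because the analysis is unpowered.
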